4.2 Rationale

4.2.1 Rationale for the Trial and Selected Subject Population

Checkpoint inhibitory drugs, such as pembrolizumab, targeting the PD-1/PD- L1 signaling pathway have been shown to promote marked antitumor immunity in patients with HL and in a subset of patients with NHL. Despite its activity and the high ORR seen in heavily pretreated patients with HL, pembrolizumab as single agent has shown only a modest CR rate of 21%.

We hypothesize that the combination of pembrolizumab with lenalidomide, an agent with complimentary immune stimulatory activity, and non-overlapping toxicity, might enhance its

therapeutic efficacy in patients with relapsed refractory HL. This novel treatment platform, which is chemotherapy free, may be highly effective for long term disease control as maintenance strategy or remission induction, and may have a role in earlier line management of frail elderly patients with relapsed disease, or who are unable to tolerate standard chemotherapy.

If this treatment strategy is safe and effective, this will provide the justification to bring this strategy in larger scale randomized trials, or to consider triplet combinations with rituximab which may ultimately demonstrate the significance of this platform in the management of multiple B cell lymphoma subtypes.

4.2.2 Rationale for Dose Selection/Regimen/Modification

4.2.2.1 Pembrolizumab

An open-label Phase I trial (Protocol 001) is being conducted to evaluate the safety and clinical activity of single agent MK-3475. The dose escalation portion of this trial evaluated three dose levels, 1 mg/kg, 3 mg/kg, and 10 mg/kg, administered every 2 weeks (Q2W) in subjects with advanced solid tumors. All three dose levels were well tolerated and no dose-limiting toxicities were observed. This first in human study of MK-3475 showed evidence of target engagement and objective evidence of tumor size reduction at all dose levels (1 mg/kg, 3 mg/kg and 10 mg/kg Q2W). No MTD has been identified to date. 10.0 mg/kg Q2W, the highest dose tested in PN001, will be the dose and schedule utilized in Cohorts A, B, C and D of this protocol to test for initial tumor activity. Recent data from other clinical studies within the MK-3475 program has shown that a lower dose of MK-3475 and a less frequent schedule may be sufficient for target engagement and clinical activity.

PK data analysis of MK-3475 administered Q2W and Q3W showed slow systemic clearance, limited volume of distribution, and a long half-life (refer to IB). Pharmacodynamic data (IL-2 release assay) suggested that peripheral target engagement is durable (>21 days). This early PK and pharmacodynamic data provides scientific rationale for testing a Q2W and Q3W dosing schedule.

A population pharmacokinetic analysis has been performed using serum concentration time data from 476 patients. Within the resulting population PK model, clearance and volume parameters of MK-3475 were found to be dependent on body weight. The relationship between clearance and body weight, with an allometric exponent of 0.59, is within the range observed for other antibodies and would support both body weight normalized dosing or a fixed dose across all body weights. MK-3475 has been found to have a wide therapeutic range based on the melanoma indication. The differences in exposure for a 200 mg fixed dose regimen relative to a 2 mg/kg Q3W body weight based regimen are anticipated to remain well within the established exposure margins of 0.5 – 5.0 for MK-3475 in the melanoma indication. The exposure margins are based on the notion of similar efficacy and

safety in melanoma at 10 mg/kg Q3W vs. the proposed dose regimen of 2 mg/kg Q3W (i.e. 5-fold higher dose and exposure). The population PK evaluation revealed that there was no significant impact of tumor burden on exposure. In addition, exposure was similar between the NSCLC and melanoma indications. Therefore, there are no anticipated changes in exposure between different indication settings.

The rationale for further exploration of 2 mg/kg and comparable doses of pembrolizumab in solid tumors is based on: 1) similar efficacy and safety of pembrolizumab when dosed at either 2 mg/kg or 10 mg/kg Q3W in melanoma patients, 2) the flat exposure-response relationships of pembrolizumab for both efficacy and safety in the dose ranges of 2 mg/kg Q3W to 10 mg/kg Q3W, 3) the lack of effect of tumor burden or indication on distribution behavior of pembrolizumab (as assessed by the population PK model) and 4) the assumption that the dynamics of pembrolizumab target engagement will not vary meaningfully with tumor type.

The choice of the 200 mg Q3W as an appropriate dose for the switch to fixed dosing is based on simulations performed using the population PK model of pembrolizumab showing that the fixed dose of 200 mg every 3 weeks will provide exposures that 1) are optimally consistent with those obtained with the 2 mg/kg dose every 3 weeks, 2) will maintain individual patient exposures in the exposure range established in melanoma as associated with maximal efficacy response and 3) will maintain individual patients exposure in the exposure range established in melanoma that are well tolerated and safe.

A fixed dose regimen will simplify the dosing regimen to be more convenient for physicians and to reduce potential for dosing errors. A fixed dosing scheme will also reduce complexity in the logistical chain at treatment facilities and reduce wastage.

4.2.2.2 Lenalidomide

Approved doses of lenalidomide for MM and MCL are 25 mg orally daily for 21 days every 28 days and for MDS 10 mg orally daily. Studies in HL have been conducted using 25mg daily as single agent on days 1-21 of a 28-day cycle²², while in NHL a lower dose of 20 mg daily on days 1-21 of a 28 cycle was shown to be safe and effective in combination with rituximab¹⁸. Variable doses from 5mg to 25 mg have been evaluated in combination with rituximab containing chemotherapy²³, with manageable toxicity profile.

In the phase 1 trial we opted to start at a lower dose of 15mg to evaluate for unexpected toxicities, particularly in this novel immunomodulatory drug-checkpoint inhibitor combination, with plan to escalate to full dose of 20mg if tolerated (as per prior phase 2 studies of combination therapy in lymphomas).

We dose Lenalidomide up to 20mg. The safety for Lenalidomide at this dose has been established in combination with Rituximab and other immune agents. Although there is now

data to support full dose Lenalidomide in combination with Pembrolizumab in multiple myeloma, given that this is a first in human study of this combination in lymphoma we do not have current plans to escalate the dose of Lenalidomide above 20mg.

4.2.3 Rationale for Endpoints

4.2.3.1 Efficacy Endpoints

In the phase 1 part of the study, the primary endpoints are safety and tolerability of the combination of pembrolizumab and lenalidomide, with determination of the MTD of lenalidomide in combination.

In the phase 2 portion of the study, the primary endpoints are overall activity assessment (CR, ORR, and PR) and of the combination of pembrolizumab with the MTD of lenalidomide in patients with RR HL.

4.2.3.2 Biomarker Research

NHL and HL are cancers in which the immune system plays a vital role in tumor tolerance and tumor growth. Evaluation of changes in circulating immune cell populations, in the tumor microenvironment abundance and composition and gene expression profiling of tumor biopsies obtained longitudinally pre, during and post therapy will provide significant and novel information regarding biological effects of this immunotherapy in NHL and HL patients, and changes in patterns based on response to or resistance to therapy.

5.0 METHODOLOGY

5.1 Entry Criteria

5.1.1 Diagnosis/Condition for Entry into the Trial

Phase 1: Pathologically confirmed relapsed or refractory B cell lymphoma. Must have relapsed after initial therapy. No restriction in number of prior lines of therapy.

Phase 2: Pathologically confirmed relapsed or refractory HL. No restriction in number of prior lines of therapy.

5.1.2 Subject Inclusion Criteria

In order to be eligible for participation in this trial, the subject must:

1. Be willing and able to provide written informed consent for the trial.

2. Be ≥ 18 years of age on day of signing informed consent.
3. Have measurable or evaluable disease, as defined in 2007 Revised Response Criteria for Malignant Lymphoma²⁴. HL patients must not be currently eligible for autologous stem cell transplant.
4. Be willing to provide either archived tumor tissue or tissue from a newly obtained core or excisional biopsy of a tumor lesion. *Newly-obtained is defined as a specimen obtained up to 6 weeks (42 days) prior to initiation of treatment on Day 1.*
5. Have a performance status of 0 to 1 on the ECOG Performance Scale.
6. Demonstrate adequate organ function as defined in Table 1, all screening labs should be performed within 14 days of treatment initiation.

Table 1 Adequate Organ Function Laboratory Values

System	Laboratory Value
Hematological	
Absolute neutrophil count (ANC)	$\geq 1,000$ /mCL if no bone marrow involvement ≥ 800 /mCL if documented bone marrow involvement
Platelets	$\geq 75,000$ / mCL if no bone marrow involvement $\geq 50,000$ / mCL if documented bone marrow involvement
Hemoglobin	≥ 8 g/dL without transfusion or EPO dependency (within 7 days of assessment)
Renal	
Serum creatinine OR Measured or calculated ^a creatinine clearance (GFR can also be used in place of creatinine or CrCl)	≤ 1.5 X upper limit of normal (ULN) OR ≥ 60 mL/min for subject with creatinine levels > 1.5 X institutional ULN
Hepatic	
Serum total bilirubin	≤ 1.5 X ULN OR
	Direct bilirubin \leq ULN for subjects with total bilirubin levels > 1.5 ULN

AST (SGOT) and ALT (SGPT)	$\leq 2.5 \times \text{ULN}$ OR $\leq 5 \times \text{ULN}$ for subjects with liver metastases
Albumin	≥ 2.5 mg/dL
Coagulation	
International Normalized Ratio (INR) or Prothrombin Time (PT)	$\leq 1.5 \times \text{ULN}$ unless subject is receiving anticoagulant therapy as long as PT or PTT is within therapeutic range of intended use of anticoagulants
Activated Partial Thromboplastin Time (aPTT)	$\leq 1.5 \times \text{ULN}$ unless subject is receiving anticoagulant therapy as long as PT or PTT is within therapeutic range of intended use of anticoagulants
^a Creatinine clearance should be calculated per institutional standard.	

7. Female subject of childbearing potential should have two negative urine or serum pregnancy test, one at 10-14 days before first dose of study drug and another within 24 hours prior to receiving the first dose of study medication. If the urine test is positive or cannot be confirmed as negative, a serum pregnancy test will be required.
8. Female subjects of childbearing potential should be willing to use 2 methods of birth control or be surgically sterile, or abstain from heterosexual activity for the course of the study through 120 days after the last dose of study medication (Reference Section 5.7.2). Subjects of childbearing potential are those who have not been surgically sterilized or have not been free from menses for > 1 year.
9. Male subjects should agree to use an adequate method of contraception starting with the first dose of study therapy through 120 days after the last dose of study therapy.

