6.2.3 Laboratory Procedures/Assessments

Details regarding specific laboratory procedures/assessments to be performed in this trial are provided below Laboratory Safety Evaluations (Complete Blood Count, Comprehensive Serum Chemistry Panel and Urinalysis)

Laboratory tests for complete Blood Count, comprehensive serum chemistry Panelurinalysis, and others are specified in Table 6.

Product: Pembrolizumab and Lenalidomide
Protocol/Amendment No.: Version 3.1 July 18th, 2017

Table 6 Laboratory Tests

Hematology	Chemistry	Urinalysis	Other
Hematocrit	Albumin	Blood	Serum β -human chorionic gonadotropin [†]
Hemoglobin	Alkaline phosphatase	Glucose	(β -hCG) [†]
Platelet count	Alanine aminotransferase (ALT)	Protein	PT (INR)
WBC (total and differential)	Aspartate aminotransferase (AST)	Specific gravity	aPTT
Red Blood Cell Count	Lactate dehydrogenase (LDH)	Microscopic exam (If abnormal)	Total triiodothyronine (T3)
Absolute Neutrophil Count	Carbon Dioxide ‡	results are noted	Free tyroxine (T4)
Absolute Lymphocyte Count	(CO₂ or biocarbonate)	Urine pregnancy test †	Thyroid stimulating hormone (TSH)
	Uric Acid		
	Calcium		
	Chloride		Blood for correlative studies
	Glucose		
	Phosphorus		
	Potassium		
	Sodium		
	Magnesium		

Product: Pembrolizumab and Lenalidomide

Protocol/Amendment No.: Version 3.1 July 18th, 2017

Hematology	Chemistry	Urinalysis	Other
	Total Bilirubin		
	Direct Bilirubin (If total bilirubin is elevated above the upper limit of normal)		
	Total protein		
	Blood Urea Nitrogen		

† Perform on women of childbearing potential only. If urine pregnancy results cannot be confirmed as negative, a serum pregnancy test will be required.
 
‡ If considered standard of care in your region.
			

Product: Pembrolizumab and Lenalidomide
Protocol/Amendment No.: Version 3.1 July 18th, 2017

Laboratory tests for screening or entry into the Second Course Phase should be performed within 10 days prior to the first dose of treatment. After Cycle 1, pre-dose laboratory procedures can be conducted up to 72 hours prior to dosing. Results must be reviewed by the investigator or qualified designee and found to be acceptable prior to each dose of trial treatment.

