6.2.4.1 Screening

6.2.4.1.1 Screening Period

The screening phase is the interval between the signing of the Informed Consent Form (IFC) and the day the subject is enrolled in the study (cycle 1 day 1). Informed consent must be obtained prior to performing any study-specific procedures. Assessments that are required to

Product: Pembrolizumab and Lenalidomide
Protocol/Amendment No.: Version 3.1 July 18th, 2017

demonstrate eligibility may be performed over 1 or more days during this phase. The maximum screening period is 30 days.

Results from the screening visit evaluations will be reviewed to confirm subject eligibility prior to enrollment/administration of study drug(s). Tests with results that fail eligibility requirements may be repeated once during the screening phase, if the Investigator believes the results to be in error or not representative. Additionally, a subject who fails screening may repeat the screening process 1 time, if the Investigator believes there has been a change in eligibility status (e.g. following recovery from an infection).

Additionally the screening period will be utilized to determine the baseline assessments of clinical condition and disease status. Tumor assessments appropriate to the type of malignancy will be performed and recorded in CRF.

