6.2.4.5 Second Course Phase (Retreatment Period)

Subjects who stop pembrolizumab with SD or better may be eligible for up to one year of additional pembrolizumab therapy if they progress after stopping study treatment. This retreatment is termed the Second Course Phase of this study and is only available if the study remains open and the subject meets the following conditions:

- **Either**
 - Stopped initial treatment with pembrolizumab after attaining an investigator-determined confirmed CR according to revised response criteria for lymphoid malignancies²⁴ and
 - Was treated for at least 24 weeks with pembrolizumab before discontinuing therapy
 - Received at least two treatments with pembrolizumab beyond the date when the initial CR was declared

OR

- Had SD, PR or CR and stopped pembrolizumab treatment after 24 months of study therapy for reasons other than disease progression or intolerability

AND

- Experienced an investigator-determined confirmed radiographic disease progression after stopping their initial treatment with pembrolizumab
- Did not receive any anti-cancer treatment since the last dose of pembrolizumab

Product: Pembrolizumab and Lenalidomide

Protocol/Amendment No.: Version 3.1 July 18th, 2017

- Has a performance status of 0 or 1 on the ECOG Performance Scale
- Demonstrates adequate organ function as detailed in Section 5.1.2
- Female subject of childbearing potential should have a negative serum or urine pregnancy test within 72 hours prior to receiving retreatment with study medication.
- Female subject of childbearing potential should be willing to use 2 methods of birth control or be surgically sterile, or abstain from heterosexual activity for the course of the study through 120 days after the last dose of study medication (Reference Section 5.7.2). Subjects of child bearing potential are those who have not been surgically sterilized or have been free from menses for > 1 year.
- Male subject should agree to use an adequate method of contraception starting with the first dose of study therapy through 120 days after the last dose of study therapy.
- Does not have a history or current evidence of any condition, therapy, or laboratory abnormality that might interfere with the subject's participation for the full duration of the trial or is not in the best interest of the subject to participate, in the opinion of the treating investigator.

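### The albumin entry limit is printed in mg/dL and so excludes nobody, and the screening-laboratory window is 14 days in Section 5.1.2 but 10 days in Section 6.2.3

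*Combined protocol and SAP*

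**What the plan says.** **Albumin.** Inclusion criterion 6 (Section 5.1.2) requires adequate organ function as set out in Table 1. The albumin line asks for 2.5 mg/dL or above. The hemoglobin line of the same table reads "≥ 8 g/dL without transfusion or EPO dependency". Section 6.2.4.5 applies the same table to patients entering the Second Course Phase: "Demonstrates adequate organ function as detailed in Section 5.1.2".

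**Timing of laboratory tests.** Four places bear on it:

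- Section 5.1.2, criterion 6: "all screening labs should be performed within 14 days of treatment initiation".
- Section 6.2.3, in the text after Table 6: "Laboratory tests for screening or entry into the Second Course Phase should be performed within 10 days prior to the first dose of treatment".
- The Trial Flow Chart (Section 6) heads its Screening column day -28 to day -1 and ticks blood count, chemistry and coagulation tests in that column.
- Section 6.2.4.1.1: "The maximum screening period is 30 days". That period runs from signature of consent to Cycle 1 Day 1, and eligibility assessments may be spread across it.

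**The concern.** An eligibility threshold has to be able to fail somebody. Serum albumin is reported on the same g/dL scale as hemoglobin, so a limit of a few mg/dL looks like a unit slip that leaves the line empty. Registration under Sections 5.2 and 5.2.5 depends on documentation that every criterion is met. A literal check of the albumin line would pass everyone, both at entry and, through the cross-reference, at Second Course entry.

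The timing rules raise a different problem. The person who verifies eligibility centrally needs one window to check against. With 14 days in one section and 10 in another, the same sample can be in order or a protocol deviation depending on which section is open. What is at stake is consistent eligibility decisions and a clean record of deviations in a small trial (26 to 29 patients).

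**Working it through.** The plan gives no calculated figure to reproduce here. The check is a unit conversion and a day-by-day comparison of the stated windows.

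**Step 1: albumin.** Input: the limit of 2.5 mg/dL (Table 1). Since 1 g = 1,000 mg,

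2.5 mg/dL ÷ 1,000 = 0.0025 g/dL.

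If g/dL was intended, the limit would be 2.5 g/dL = 2,500 mg/dL, and 2,500 ÷ 2.5 = 1,000 times the printed value.

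The documents give no albumin reference range, so I assume patient values from 1.0 to 5.0 g/dL:

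- Low end: 1.0 g/dL = 1,000 mg/dL; 1,000 ÷ 2.5 = 400 times the limit.
- High end: 5.0 g/dL = 5,000 mg/dL; 5,000 ÷ 2.5 = 2,000 times the limit.

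No value in that range fails.

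**Step 2: windows.** Inputs: 10 days (6.2.3), 14 days (5.1.2), day -28 to -1 (flow chart) and 30 days (6.2.4.1.1). I take treatment initiation, first dose and Cycle 1 Day 1 to be the same day, and read the 10-day sentence as covering initial screening.

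| Day of sample | 10 days (6.2.3) | 14 days (5.1.2) | Chart, -28 to -1 | 30 days (6.2.4.1.1) |
|---|---|---|---|---|
| -10 to -1 | meets | meets | meets | meets |
| -14 to -11 | fails | meets | meets | meets |
| -28 to -15 | fails | fails | meets | meets |
| -30 to -29 | fails | fails | fails | meets |

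The two rules written specifically for laboratory tests disagree on 14 - 10 = 4 days, namely -14 to -11. The two general screening periods disagree on 30 - 28 = 2 days, namely -30 and -29.

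**Step 3: is the chart a third laboratory rule?** Its window heads the whole Screening column, not the laboratory rows. A footnote narrows the timing of the pregnancy test; in the text available, no footnote does so for blood count, chemistry or coagulation. The chart therefore does not repeat either laboratory limit, but it does not set a 28-day laboratory rule either.

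**The case against.** The case for treating this as editorial is strong in several respects.

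- **Only one line of Table 1 is affected.** A reader might infer that the organ-function limits as a whole cannot be applied. They can: the neutrophil, platelet, hemoglobin, renal, bilirubin, transaminase and coagulation lines are all usable.
- **A site would probably recognise the slip.** Nothing in the documents suggests that anyone would apply mg/dL literally. That stands, but the printed criterion is still the one that has to be verified.
- **The windows are nested.** Samples within 10 days of first dose satisfy every rule, and a 28-day visit window can contain a tighter laboratory limit. A reader might count three contradictory laboratory windows; the text supports one direct mismatch, 14 against 10 days.
- **The 10-day sentence is ambiguous.** It could be read as covering only the Second Course Phase. On that reading the mismatch at initial screening disappears. The wording would still need clarifying, because Second Course entry points back to Section 5.1.2, whose criterion carries 14 days.
- **Registration is central.** A reader might infer that the centres will enrol under different rules. Section 5.2.5 has one Quality Assurance Unit review the documents before a study number is issued, so divergence between sites is not shown.
- **Harm to dose finding is not shown.** It is tempting to argue that out-of-date counts after recent chemotherapy would distort the count of dose-limiting toxicities and reverse an escalation decision. The documents do not support this. Section 5.1.3, exclusion 6, bars patients who have not recovered from earlier agents. Blood count and chemistry are scheduled on Cycle 1 Day 1, and Section 6.2.3 requires results to be judged acceptable before each dose. Section 5.3.1.3 requires hematologic events to be at least possibly attributable to the regimen. The argument would also apply to a 14-day window used with complete consistency, so it does not follow from the contradiction.

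**Conclusion.** The point holds in limited form. As printed, the albumin limit is 0.0025 g/dL and cannot exclude a patient, at entry or at Second Course entry. This rests on the literal unit and on an assumed albumin range of 1.0 to 5.0 g/dL; the thousand-fold factor also assumes that g/dL was meant, which only the sponsor can confirm.

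On the ordinary reading of Section 6.2.3, the laboratory window is inconsistent for samples on four days, -14 to -11. The general screening period differs by two days between the flow chart and Section 6.2.4.1.1.

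The consequence is for the consistency and verifiability of eligibility. Sample size, power, type I error and the primary endpoint are untouched, and no effect on dose-limiting toxicity counts or escalation is demonstrated.

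**What to change.** 1. The sponsor confirms the intended albumin unit and corrects Table 1. The cross-reference in Section 6.2.4.5 then carries the correction to Second Course entry.
2. Sections 5.1.2 and 6.2.3 and the Trial Flow Chart are reconciled to one laboratory window, shown in the chart as a footnote to the laboratory rows. Section 6.2.3 should say whether its 10-day sentence applies to initial screening, to Second Course entry, or to both.
3. The flow chart and Section 6.2.4.1.1 are reconciled to one screening period.

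Which window and which period to keep is for the sponsor to decide. The change is wording in four places (5.1.2, 6.2.3, 6.2.4.1.1 and the chart), and reconciling the text adds no visit or scheduled test. If a shorter laboratory window is chosen, some patients may need a repeat sample before first dose.

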9. Has active autoimmune disease that has required systemic treatment in the past 2 years (i.e. with use of disease modifying agents, corticosteroids or immunosuppressive drugs). Replacement therapy (eg., thyroxine, insulin, or physiologic corticosteroid replacement therapy for adrenal or pituitary insufficiency, etc.) is not considered a form of systemic treatment.
10. Has known history of, or any evidence of active, non-infectious pneumonitis.
11. Has an active infection requiring systemic therapy.
12. Has a history or current evidence of any condition, therapy, or laboratory abnormality that might confound the results of the trial, interfere with the subject's participation

- for the full duration of the trial, or is not in the best interest of the subject to participate, in the opinion of the treating investigator.
13. Has known psychiatric or substance abuse disorders that would interfere with cooperation with the requirements of the trial.
 14. Is pregnant or breastfeeding, or expecting to conceive or father children within the projected duration of the trial, starting with the screening visit through 120 days after the last dose of trial treatment.
 15. Has received prior therapy with an anti-PD-1, anti-PD-L1, or anti-PD-L2 agent.
 16. Has a known history of Human Immunodeficiency Virus (HIV) (HIV 1/2 antibodies).
 17. Has known active Hepatitis B (e.g., HBsAg reactive) or Hepatitis C (e.g., HCV RNA [qualitative] is detected), or other active viral hepatitis. Patients with treated and resolved hepatitis B or C are eligible. Patients with active liver disease, except liver abnormalities directly attributable to lymphoma are ineligible,
 18. Has received a live vaccine within 30 days of planned start of study therapy.

Note: Seasonal influenza vaccines for injection are generally inactivated flu vaccines and are allowed; however intranasal influenza vaccines (e.g., Flu-Mist®) are live attenuated vaccines, and are not allowed.

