5.6.2 Contraception

Lenalidomide may cause severe birth defects or death of the fetus if used during pregnancy. Lenalidomide is similar to thalidomide, which causes life-threatening birth defects. Pembrolizumab may have adverse effects on a fetus in utero, too. Furthermore, it is not known if pembrolizumab has transient adverse effects on the composition of sperm. Non-pregnant, non-breast-feeding women may be enrolled if they are willing to use 2 methods of birth control or are considered highly unlikely to conceive. Highly unlikely to conceive is defined as 1) surgically sterilized, or 2) postmenopausal (a woman who is ≥ 45 years of age and has not had menses for greater than 1 year will be considered postmenopausal), or 3) not heterosexually active for the duration of the study. The two birth control methods can be either two barrier methods or a barrier method plus a hormonal method to prevent pregnancy. Subjects should start using birth control from study Visit 1 throughout the study period up to 120 days after the last dose of study therapy.

The following are considered adequate barrier methods of contraception: diaphragm, condom (by the partner), copper intrauterine device, sponge, or spermicide. Appropriate hormonal contraceptives will include any registered and marketed contraceptive agent that contains an estrogen and/or a progestational agent (including oral, subcutaneous, intrauterine, or intramuscular agents).

Subjects should be informed that taking the study medication may involve unknown risks to the fetus (unborn baby) if pregnancy were to occur during the study. In order to participate in the study they must adhere to the contraception requirement (described above) for the duration of the study and during the follow-up period defined in section 7.2.2-Reporting of Pregnancy and Lactation to the Sponsor and to Merck. If there is any question that a subject will not reliably comply with the requirements for contraception, that subject should not be entered into the study.

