		^a Every week +/- 3 days; except Cycle 1 ^b Day 1 of 21 day cycle ^c Day 1-14 of 21 day cycle ^Λ Every 12 weeks +/- 1 week ^β Biopsy while on therapy is optional ^c For women of child bearing potential: Pregnancy test is required 10-14 days prior to first dose of study drug AND a second pregnancy test is required within 24 hours before first dose of study drug														

Product: Pembrolizumab and Lenalidomide
Protocol/Amendment No.: Version 3.1 July 18th, 2017

TRIAL PROCEDURES

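### Inclusion item 8 omits the age-45 condition that Section 5.6.2 attaches to amenorrhoea, so the protocol disagrees with itself on who is protected before lenalidomide

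*Combined protocol and SAP*

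**What the plan says.** Section 5.1.2, item 7, requires two negative pregnancy tests before the first dose for women of childbearing potential. Item 8 requires two methods of birth control, surgical sterility or abstinence from the same group, and then defines the group: "Subjects of childbearing potential are those who have not been surgically sterilized or have not been free from menses for > 1 year".

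Section 5.6.2 approaches contraception from the other side: "women may be enrolled if they are willing to use 2 methods of birth control or are considered highly unlikely to conceive". The second category covers women who are surgically sterilised, not heterosexually active, or postmenopausal, and the last is limited to "a woman who is ≥ 45 years of age and has not had menses for greater than 1 year".

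The other testing rules use item 8's label without redefining it. The flow-chart footnote begins "For women of child bearing potential: Pregnancy test is required 10-14 days prior to first dose of study drug", and the Table 6 footnote in Section 6.2.3 says "Perform on women of childbearing potential only".

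Two further places bear on the point. Item 8 cites a Section 5.7.2, which does not exist: 5.7.1 is followed by 5.8, and contraception is in 5.6.2. Section 6.2.4.5, on pembrolizumab retreatment, repeats that reference and gives another definition: "Subjects of child bearing potential are those who have not been surgically sterilized or have been free from menses for > 1 year". The second *not* has gone.

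**The concern.** The protocol itself judges, in 5.6.2, that a year without menses before age 45 is not enough to rule out conception. The eligibility criterion leaves that judgement out. It also joins two negative conditions with *or*, which can mean either that both must hold or that one is enough.

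The stake is fetal exposure to lenalidomide, which 5.6.2 warns can malform or kill a fetus. Women under 45 are likely to be common here: the single-agent pembrolizumab Hodgkin cohort described in Section 4.1.3 had a median age of 32 (range 20 to 67). Several institutions enrol, so different sites may parse the sentence differently.

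**Working it through.** No statistical figure is involved; this is a check of definitions. I listed every combination of three attributes for a heterosexually active woman and applied each rule. Abstinence is set aside because both sections accept it in place of contraception.

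Let S = surgically sterilised, A = age 45 or over, M = no menses for more than 1 year.

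- Item 8, ordinary reading (neither condition met): (not S) and (not M)
- Item 8, literal reading: (not S) or (not M)
- Section 6.2.4.5, literal reading: (not S) or M
- Section 5.6.2, contraception needed: (not S) and not (A and M)

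| S | A | M | Item 8 ordinary | Item 8 literal | 6.2.4.5 literal | 5.6.2 |
|---|---|---|---|---|---|---|
| no | no | no | yes | yes | yes | yes |
| no | yes | no | yes | yes | yes | yes |
| no | no | yes | **no** | yes | yes | yes |
| no | yes | yes | no | **yes** | **yes** | no |
| yes | no | no | no | **yes** | no | no |
| yes | yes | no | no | **yes** | no | no |
| yes | no | yes | no | no | **yes** | no |
| yes | yes | yes | no | no | **yes** | no |

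Bold marks disagreement with 5.6.2.

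- **Ordinary reading of item 8:** 1 of 8 disagrees, and there item 8 is less protective: unsterilised, under 45, amenorrhoeic.
- **Literal reading of item 8:** 3 of 8 disagree, all over-inclusive: the unsterilised amenorrhoeic woman of 45 or over, and sterilised women, at either age, without a year of amenorrhoea.
- **Section 6.2.4.5, literal:** 3 of 8 disagree, all over-inclusive.
- **The two readings of item 8 against each other:** they differ in 4 of 8 (rows 3 to 6).

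These counts compare the childbearing-potential label with 5.6.2's contraception duty. Item 8 and 6.2.4.5 both accept surgical sterility in place of contraception. For contraception alone, the sterilised rows therefore drop out and each count of 3 becomes 3 − 2 = 1. For those rows only testing is added.

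The remaining question is whether anything else catches the woman in row 3 under the ordinary reading.

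- **Contraception:** yes, for a site that applies 5.6.2, since it is a condition of enrolment.
- **Testing:** no. Section 5.6.2 has no testing rule. Item 7, the flow-chart footnote and Table 6 all depend on item 8's label. Exclusion 14 in Section 5.1.3 ("Is pregnant or breastfeeding, or expecting to conceive or father children within the projected duration of the trial") bars a pregnant woman but names no test. She would miss the two tests before dosing and the later ones scheduled under the same label.

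**The case against.** The strongest reply is that item 8, taken exactly as written, covers this woman, so she is tested and must use contraception. There is some textual support: item 8's allowance for surgical sterility would be redundant if sterilised women were already outside the group. The literal reading is indeed the safe one for her, but the documents do not say which reading sites use, and the literal one still conflicts with 5.6.2 for unsterilised postmenopausal women.

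A second reply is that 5.1.2 and 5.6.2 apply together, so a site following the stricter rule would require contraception from her anyway. That stands for contraception. It does not supply a pregnancy test. Section 5.2 also sends investigators to 5.1.2 and 5.1.3 to determine eligibility, without naming 5.6.2, and the cross-reference in item 8 fails.

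A third is that Sections 5.2 and 5.2.5 require documents verifying every criterion, with central review for the additional sites, and non-pregnancy is one of the criteria. This lowers the risk, but no form of proof is named for a woman classed as outside the group.

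Finally, the wrong section number and the slip in 6.2.4.5 are editorial, and the slip concerns pembrolizumab retreatment and errs toward over-inclusion. Both are secondary.

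**Conclusion.** The concern holds. Item 8 lacks the age condition, its *or* is ambiguous, and neither reading reproduces 5.6.2. The harmful part is narrow: one profile of eight, on one of two readings, with testing as the unprotected step, plus contraception at any site that screens from 5.1.2 alone. These are profiles, not patients. The documents give no rate of amenorrhoea and no expected number of such women, so the count among the 26 to 29 planned patients may be small or zero.

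It should still be corrected. The error is in a safety criterion for a teratogenic drug, and the protocol already contains the rule that resolves it. Nothing in the sample size, endpoints or analysis is affected.

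**What to change.** In 5.1.2, item 8, define a woman of childbearing potential as one who is neither surgically sterilised nor postmenopausal, with postmenopausal meaning 45 or older and more than 1 year without menses. Apply that definition to pregnancy testing and contraception in 5.1.2, 5.6.2, 6.2.4.5, the flow-chart footnote and Table 6. State that abstinence waives contraception but not testing. In 6.2.4.5, replace the faulty sentence with a reference to item 8. Correct the Section 5.7.2 reference to 5.6.2 in both places.

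The cost is a wording amendment, with matching changes to any eligibility checklist that repeats item 8, and at most a few extra pregnancy tests.
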